4.0 Patient Eligibility

Inclusion criteria:

1. Chronic lymphocytic leukemia (CLL) patients with IgG less than 500 mg/dl with/without symptoms who are either untreated or previously treated, regardless of response, at least 6 months from prior therapy (including mAb).
2. ECOG/WHO performance status of 0-2.
3. Adequate renal functions as indicated by serum creatinine ≤ 2 mg/dl.
4. Adequate hepatic function indicated as total bilirubin ≤ 2 mg/dl and ALT \leq two times the upper limit of normal.
5. Disease free of prior malignancies for 3 years with exception of currently treated basal cell, squamous cell carcinoma of the skin, or carcinoma "in situ" of the cervix or breast. Patients with malignancies with indolent behavior such as prostate cancer treated with radiation or surgery can be enrolled in the study as long as they have a reasonable expectation to have been cured with the treatment modality received.
6. Females of childbearing potential (FCBP). A female of childbearing potential is a sexually mature woman who: 1) has not undergone a hysterectomy or bilateral oophorectomy; or 2) has not been naturally postmenopausal for at least 24 consecutive months (i.e., has not had menses at any time in the preceding 24 consecutive months).

7. FCBP must have a negative serum or urine pregnancy test with a sensitivity of at least 50 mIU/mL within 10 – 14 days prior to and again within 24 hours of starting lenalidomide and must either commit to continued abstinence from heterosexual intercourse or begin **TWO** acceptable methods of birth control, one highly effective method and one additional effective method **AT THE SAME TIME**, at least 28 days before she starts taking lenalidomide.
8. FCBP must also agree to ongoing pregnancy testing (weekly for the first four weeks and then every 28 days while on therapy and at discontinuation of treatment).
9. Men must agree to use a latex condom during sexual contact with a FCBP even if they have had a successful vasectomy. All patients must be counseled at a minimum of every 28 days about pregnancy precautions and risks of fetal exposure.
10. Patients must be 18 years of age or older.
11. All study participants must be registered into the mandatory Revlimid® program, and be willing and able to comply with the requirements of Revlimid®.

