8.0 Criteria for Response

Response criteria -

Ig response – Only IgG levels will be considered for response. IgG levels will be measured as mg/dL by nephelometry (normal range 700-1,600 mg/dL). Response will consist of normalization or improvement by 25% of baseline levels at 6 months during therapy.

Response criteria for the immunization –

Quadrivalent Influenza Vaccine (Fluvarix). HI assay was performed as previously described. Samples were assayed at baseline, 4 weeks (+/- 2 week) and 3 months (+/- 3 weeks) post-vaccination. Response or protection to influenza vaccination was defined as > 40 HU or a fourfold increase in HI titer at 4 weeks (+/- 2 week) and 3 months (+/- 3 weeks) post vaccination, against any of the three strains.

Assessment of the functionality of antigen-specific CD8+ and CD4+ T cells will be performed by intracellular cytokine staining for interferon (INF)-g and tumor necrosis factor (TNF)-a and evaluation of CD154 expression and CD107a cytotoxicity. In brief, PBMCs will be thawed and stimulated for 24 hours with or without the seasonal

influenza vaccine [A/Brisbane/59/2007(H1N1)-, A/Brisbane/10/2007 (H3N2)- and B/Florida/30/2008-like strain; CSL Biotherapies, Hattersheim, Germany]. A response will be considered positive if the % of antigen-specific IFN- γ -, TNF- α -, or CD107a-expressing T cells is ≥ 2 -fold higher than background (unstimulated PBMCs) and if there is a minimum of 0.05% antigen-specific T cells (after subtracting the background or FMO fluorescence minus one).

Pneumococcal Polysaccharide Vaccine - Seroconversion will be defined as at least a two fold increase in levels of antipneumococcal capsular polysaccharide (PCP) IgG antibody or achievement of concentration of $>0.5\mu\text{g/ml}$ in anti-pneumococcal capsular polysaccharide antibody titer (against 6 serotypes). They will be measured before, 4 weeks (+/- 2 week) and 3 months (+/- 3 weeks) post vaccination using ELISA and at the end of the study.

Exploratory Endpoints:

1. Infection rates of influenza or Pneumococcal pneumonia will be recorded during the study.
2. Sustained immunoglobulin responses will be recorded along with serological responses to both the vaccines.
3. Sera will be analysed for cytokine levels and properdin levels.

Correlative studies –

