9.0 Statistical design with exploratory endpoints –

The primary efficacy endpoint is IgG response, defined as having improvement in IgG level by at least 25% at 6 months, compared to baseline. We are targeting an IgG response rate of 50% and we would not be interested in pursuing further if the IgG response rate is 20% or lower. Using Simon's optimal two-stage design, we will enroll 12 patients in the first stage and the trial will be stopped if there are 3 or less IgG responders among the first 12 patients. If there are 4 or more responders, we will continue the enrollment until 31 patients are reached. The effect of lenalidomide is demonstrated and worth pursuing further if among the total 31 patients, at least 10 patients achieve IgG response. This design is based on a type I error rate of 0.025 and a 90% power. Under the null hypothesis, the probability of early termination is 79% and the expected sample size is 16 patients. Patient enrollment will be suspended if there are not at least 3 IgG responders in the first 12 patients and not all 12 patients have been evaluated at 6 months. To account for a potential 10% early drop-out rate, we will enroll 35 patients so as to have 31 patients with both baseline and 6-month evaluations on IgG. Potential reasons for early dropouts are patients' choice, inability to return to our center or changes in CLL status that may require a different intervention. Sensitivity

analysis will be performed to assess the impact of early dropouts. For example, we will analyze the data counting early dropouts either as "failures" (the most conservative approach) or as "missing" (thus, excluded from the analysis) and evaluate the response rate in both scenarios. Also, since the treatment requires at least 3 months of therapy before seeing an effect on immunoglobulin levels, we will also perform a secondary analysis by including only those patients who have been treated for at least 3 months, while counting those early dropouts between 3 and 6 months as "failures".

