Lenalidomide-related toxicity (defined as any grade 3 or greater non-hematological toxicity) will be monitored using the method of Thall, Simon and Estey [16] and the study will be terminated early if toxicity occurs in more than 40% of patients. Specifically, denoting the probability of toxicity by p , the study will be stopped early if $\text{Prob}(p > 0.40 \text{ data}) > .95$. The above decision criterion will be applied in cohort size of 5. Assuming a beta (.4, .6) priori for p , the above decision criterion implies that we will stop the trial according to the table below. For example, the trial will be terminated if 4 or more patients experienced toxicities among the first 5 patients.

Number of patients	Number of patients with toxicities is at least
5	4
10	7
15	10
20	12
25	15
30	17

The operating characteristics of this study design based on 10,000 simulations are illustrated in Table 2.

Table 2. Operating Characteristics for Toxicity Monitoring Rule.

True toxicity rate	Prob (stop early)	Sample Size 25 th , 50 th and 75 th percentiles
0.20	0.006	35, 35, 35
0.30	0.039	35, 35, 35
0.40	0.152	35, 35, 35
0.50	0.447	10, 35, 35
0.60	0.808	5, 15, 30

For the primary analysis, we will estimate the rate of IgG response along with the 95% confidence interval. As secondary analyses, we will also estimate the rates of Pneumococcus and Influenza seroconversion response, as defined in the response criteria section, and the corresponding 95% confidence intervals. The study will be considered positive in regard to the secondary endpoints if seroconversion is observed in 60% or more of the subjects for at least one of the vaccinations given. Similar method will be used to estimate the rate of influenza or Pneumococcal pneumonia. The duration of IgG response will be estimated using the Kaplan-Meier method. The cytokine levels and serum properdin levels will be summarized using descriptive statistics and will be compared between IgG responders and non-responders using two-sample t-test or Wilcoxon rank-sum test, as appropriate.

Amendments, Deviations, Regulatory

Protocol Amendments

Any amendment to this protocol must be agreed to by the Principal Investigator and reviewed by Celgene. Amendments should only be submitted to IRB after consideration of Celgene review. Written verification of IRB approval will be obtained before any amendment is implemented.

Protocol Deviations

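### The exploratory cytokine and properdin analysis uses IgG recovery only as a yes/no split at a 25% rise; a pre-specified analysis of the continuous IgG change should be added

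*Protocol*

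**What the plan says.** The last sentence of protocol section 9.0, and of the SAP, has cytokine and properdin levels summarised descriptively; they "will be compared between IgG responders and non-responders using two-sample t-test or Wilcoxon rank-sum test, as appropriate". The analytes are properdin, IFN-gamma, IL-10, TNF-alpha, BAFF, IL-8, CCL3 and CCL4 (section 8.0, correlative studies).

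A responder is "defined as having improvement in IgG level by at least 25% at 6 months, compared to baseline" (section 9.0). Section 8.0 words it slightly differently: "Response will consist of normalization or improvement by 25% of baseline levels at 6 months during therapy". The extra normalization route does not alter the split. Entry requires "Chronic lymphocytic leukemia (CLL) patients with IgG less than 500 mg/dl", and section 8.0 puts the lower limit of normal at 700 mg/dL, so normalization means a rise of more than 700/500 - 1 = 40%.

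IgG is a nephelometry value in mg/dL (section 8.0). Section 9.0 enrolls 35 patients "so as to have 31 patients with both baseline and 6-month evaluations on IgG". No analysis in either document uses the size of the IgG change.

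Section 8.0 lists the cytokine and properdin work as exploratory and correlative. Section 1.0 lists cytokines among the non-IgG immune functions that the trial sets out to evaluate.

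**The concern.** The 25% cut is needed for the go/no-go decision, which counts responders. The marker analysis asks something else: whether marker levels go with IgG recovery. Here the cut puts a 24% rise with a fall, and a 26% rise with a doubling. The documents give no reason to expect marker biology to change at 25%.

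At stake is the power of an exploratory analysis in at most 31 evaluable patients. If the relation is graded, the split test needs a stronger association to detect it than a test on the measured change would.

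**Working it through.** **Inputs from the documents.** Target response rate 50%, null rate 20%, 12 patients in stage 1 with a stop at 3 or fewer responders, 31 evaluable patients, stated success threshold 10 of 31 (all section 9.0).

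**Assumptions.** The documents give no marker effect size, no IgG distribution and no test level for this analysis. I assume a linear relation between the marker and an approximately normal log IgG change, a correlation of 0.4-0.5, and two-sided 5% tests for each analyte without multiplicity adjustment.

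**1. The plan's own figures.** At a true 20%, the probabilities of 0, 1, 2 and 3 responders in 12 are 0.0687, 0.2062, 0.2835 and 0.2362. They sum to 0.795, the stated 79% chance of early termination. Expected size is 12 + 0.205 x 19 = 15.9, the stated 16. Dropout: 31/0.9 = 34.4, hence 35. All reproduce.

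**2. Response share when 31 patients are reached at a true 20%.** The unconditional stage 1 mean is 12 x 0.2 = 2.4. Outcomes of 3 or fewer contribute 0.2062 + 2 x 0.2835 + 3 x 0.2362 = 1.482. The mean given continuation is (2.4 - 1.482)/0.2054 = 4.47. Adding 19 x 0.2 = 3.8 gives 8.27 of 31, or 27%. Six or fewer responders of 31 then occurs about 18% of the time.

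**3. Information kept by the split.** Relative to the continuous analysis, efficiency is phi(z_p)^2 / [p(1 - p)], where p is the response share, z_p its normal quantile and phi the normal density.

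| Response share | Calculation | Efficiency | Equivalent patients of 31 |
|---|---|---|---|
| 50% (target) | 0.3989^2 / 0.25 | 0.637 | 19.7 |
| 32% (10/31) | 0.3588^2 / 0.2185 | 0.589 | 18.3 |
| 27% (step 2) | 0.3286^2 / 0.1956 | 0.552 | 17.1 |
| 20% (null) | 0.2800^2 / 0.16 | 0.490 | 15.2 |

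For Wilcoxon against Spearman, multiply by pi/3: 0.637 becomes 0.667 and 0.490 becomes 0.513.

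**4. Power at n = 31** (simulation, 20,000 runs, bivariate normal; Pearson against two-sample t-test).

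| Correlation | Continuous | Split, 50% responders | Split, 32% | Split, 20% |
|---|---|---|---|---|
| 0.4 | 62-63% | 43% | 40% | 34% |
| 0.5 | 84% | 63% | 59% | 50% |

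The rank pair at correlation 0.5 and 50% responders is about 79% (Spearman) against 60% (Wilcoxon).

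**5. A different model.** Suppose the marker differs by true class (responder or unchanged) by 1.1 SD and does not track the size of the rise. Half the patients are true responders; log IgG change has mean 0.5 or 0.7 in them and 0 in the others. (4,000 runs, n = 31.)
- SD of log IgG change 0.265: t-test 44% against Pearson 47% (mean 0.5), and 58% against 60% (mean 0.7). Wilcoxon 42% against Spearman 48%, and 55% against 59%. The continuous test gains 2-6 points.
- SD 0.15, mean 0.5: t-test 73% against Pearson 68%; Wilcoxon 70% against Spearman 64%. The split wins by 5-6 points.

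**The case against.** **The loss depends on the model.** This stands. Step 5 shows the advantage shrinking to a few points or reversing when the marker follows responder class. The documents do not say which model is right. A graded relation is a reasonable default, and that is all that can be claimed.

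**The comparison is legitimate.** This also stands. Whether markers differ between those who met the primary endpoint and those who did not is interpretable, so there is no case for removing the test or reducing it to description.

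**A reader might infer that half the information is lost.** That pairs the null rate with a full sample: section 9.0 says "we would not be interested in pursuing further if the IgG response rate is 20% or lower", and efficiency at 20% is 0.490. But at that rate the trial stops at stage 1 about 79% of the time, leaving about 12 patients, too few for either analysis to be of much use. If it does continue, the expected share is about 27% and efficiency about 0.55. The 49% figure is an extreme case.

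**A reader might also infer that a real link will probably be missed and reported as absent.** The documents do not support this. At an assumed correlation of 0.5 the split still has 50-63% power, and power falls below half only at the weaker assumed correlation. Nothing in the plan says that a non-significant result will be reported as no association.

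**The continuous measure has its own difficulties.** Under section 3.0, patients whose IgG has risen at 3 months enter an on/off schedule while the others move to daily dosing, so month-6 IgG is read under differing treatment. Responder status at month 6 has the same problem, so this does not favour the split, but it limits interpretation of either analysis.

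**Conclusion.** The point holds as a cheap gain in efficiency for an exploratory analysis. Under a linear relation with roughly normal log IgG change, the split keeps about 64% of the information at the target response rate and 55-59% at response shares of 27-32%. At 50% responders and an assumed correlation of 0.4-0.5, that costs about 19-21 points of power (62% against 43%; 84% against 63%). These powers rest on assumed correlations, unadjusted 5% tests and the full 31 patients. If markers differ only by class, the gain is small or reversed.

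A reader might take this as a weakness in the trial's main result. It is not: no decision rule uses the marker analysis, and the primary and secondary conclusions are unaffected.

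**What to change.** In the last sentence of protocol section 9.0 and of the SAP, add: *The association of each cytokine and of properdin, measured at baseline, with log(month-6 IgG / baseline IgG) will be estimated by Spearman rank correlation with a 95% confidence interval. This is the main association analysis; the comparison between IgG responders and non-responders will be reported alongside it as supportive.*

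The sampling time must be named, because section 9.0 names none and the later sera are tied to influenza vaccination, which is seasonal and not fixed relative to month 6. Baseline is a sensible choice: section 5.0 stores a sample then, whereas later samples may be missing for non-responders because section 6.0 removes patients for lack of response. The wording should be settled before the stored sera are analysed.

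The cost is one sentence, with no new samples, visits or patients. There are two downsides. Patients without a month-6 IgG drop out of the correlation, though they could be counted as non-responders in the supportive comparison. The report should also note that month-6 IgG was measured under differing treatment schedules. The primary endpoint and the Simon rule stay as they are.

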9.0 Statistical design with exploratory endpoints –

The primary efficacy endpoint is IgG response, defined as having improvement in IgG level by at least 25% at 6 months, compared to baseline. We are targeting an IgG response rate of 50% and we would not be interested in pursuing further if the IgG response rate is 20% or lower. Using Simon's optimal two-stage design, we will enroll 12 patients in the first stage and the trial will be stopped if there are 3 or less IgG responders among the first 12 patients. If there are 4 or more responders, we will continue the enrollment until 31 patients are reached. The effect of lenalidomide is demonstrated and worth pursuing further if among the total 31 patients, at least 10 patients achieve IgG response. This design is based on a type I error rate of 0.025 and a 90% power. Under the null hypothesis, the probability of early termination is 79% and the expected sample size is 16 patients. Patient enrollment will be suspended if there are not at least 3 IgG responders in the first 12 patients and not all 12 patients have been evaluated at 6 months. To account for a potential 10% early drop-out rate, we will enroll 35 patients so as to have 31 patients with both baseline and 6-month evaluations on IgG. Potential reasons for early dropouts are patients' choice, inability to return to our center or changes in CLL status that may require a different intervention. Sensitivity

analysis will be performed to assess the impact of early dropouts. For example, we will analyze the data counting early dropouts either as "failures" (the most conservative approach) or as "missing" (thus, excluded from the analysis) and evaluate the response rate in both scenarios. Also, since the treatment requires at least 3 months of therapy before seeing an effect on immunoglobulin levels, we will also perform a secondary analysis by including only those patients who have been treated for at least 3 months, while counting those early dropouts between 3 and 6 months as "failures".

Lenalidomide-related toxicity (defined as any grade 3 or greater non-hematological toxicity) will be monitored using the method of Thall, Simon and Estey [16] and the study will be terminated early if toxicity occurs in more than 40% of patients. Specifically, denoting the probability of toxicity by p , the study will be stopped early if $\text{Prob}(p > 0.40 \text{ data}) > .95$. The above decision criterion will be applied in cohort size of 5. Assuming a beta (.4, .6) priori for p , the above decision criterion implies that we will stop the trial according to the table below. For example, the trial will be terminated if 4 or more patients experienced toxicities among the first 5 patients.

Number of patients	Number of patients with toxicities is at least
5	4
10	7
15	10
20	12
25	15
30	17

The operating characteristics of this study design based on 10,000 simulations are illustrated in Table 2.

Table 2. Operating Characteristics for Toxicity Monitoring Rule.

True toxicity rate	Prob (stop early)	Sample Size 25 th , 50 th and 75 th percentiles
0.20	0.006	35, 35, 35
0.30	0.039	35, 35, 35
0.40	0.152	35, 35, 35
0.50	0.447	10, 35, 35
0.60	0.808	5, 15, 30

For the primary analysis, we will estimate the rate of IgG response along with the 95% confidence interval. As secondary analyses, we will also estimate the rates of Pneumococcus and Influenza seroconversion response, as defined in the response criteria section, and the corresponding 95% confidence intervals. The study will be considered positive in regard to the secondary endpoints if seroconversion is observed in 60% or more of the subjects for at least one of the vaccinations given. Similar method will be used to estimate the rate of influenza or Pneumococcal pneumonia. The duration of IgG response will be estimated using the Kaplan-Meier method. The cytokine levels and serum properdin levels will be summarized using descriptive statistics and will be compared between IgG responders and non-responders using two-sample t-test or Wilcoxon rank-sum test, as appropriate.
